# 5. TREATMENT ALLOCATION AND BLINDING

#### 5.1. Randomization

Central randomization will be implemented in this study. Patients will be randomized based on a computer-generated randomization schedule prepared by or under the supervision of the sponsor before the study. The randomization will be balanced by using randomly permuted blocks and will be stratified by region (United States, all other countries). The Interactive Web Response System (IWRS) will assign a unique treatment code, which will dictate the treatment assignment and matching study drug kit for the patient.

Patients will be randomized at Baseline to 1 of 4 treatment arms in a 2:2:1:1 ratio as follows:

- MIN-101 64 mg for the entire study, or
- MIN-101 32 mg for the entire study, or
- Placebo for 12 weeks followed by MIN-101 64 mg dose during the open-label extension phase, or
- Placebo for 12 weeks followed by MIN-101 32 mg dose during the open-label extension phase.

The investigator will not be provided with randomization codes. The codes will be maintained within the IWRS, which has the functionality to allow the investigator to break the blind for an individual patient, if needed.

# 5.2. Blinding

Under normal circumstances, the blind should not be broken until all patients have completed the double-blind phase of study and the database is finalized. Otherwise, the blind should be broken only if specific emergency treatment/course of action would be dictated by knowing the treatment the patient is receiving. In such cases, the investigator may in an emergency determine the identity of the treatment by IWRS. Telephone contact with the sponsor or its designee will be available 24 hours per day, 7 days per week.

In the event the blind is broken, the sponsor must be informed as soon as possible. The date, time, and reason for the unblinding must be documented by the investigator, in the appropriate section of the eCRF, and in the source document. The documentation received from the IWRS indicating the code break must be retained with the patient's source documents in a secure manner (e.g., sealed envelope) so as not to unblind the treatment assignment to the study site, sponsor/contract research organization personnel. The investigator is also advised not to reveal the study treatment assignment to the study site or sponsor personnel.

# 6. DOSAGE AND ADMINISTRATION

On Day 1 (Visit 4) of the double-blind treatment phase, patients will be randomized to receive once daily MIN-101 32 mg or 64 mg doses, or placebo for 12 weeks, followed by a 40-week open-label treatment extension phase when all patients will receive MIN-101 (Table 3).

Study drug will be packaged using a double-blind design. Drug supplies of the study drug will be packaged using blister card each containing 9 tablets, the equivalent of 1 week of treatment plus 2 tablets (security margin). The patients will receive sufficient medication at the scheduled visits per the Time and Events Schedule. Daily dosing will consist of 1 tablet each containing the intended dose. Placebo and MIN-101 tablets are identically matched in appearance and the MIN-101 tablets are available in 32 mg and 64 mg strength.

	Tablet Strength		Total Number of Tablets		
Treatment/ daily dosage	MIN-101 (mg)	No. of placebo tablets	During 12-week Double- blind Phase	MIN-101 Tablets During 40-week Open-label Phase	Total MIN-101 Tablets Administered
Placebo then 32 mg	0 mg	1	84 (0 mg)	280 (32 mg)	280 (32 mg)
Placebo then 64 mg	0 mg	1	84 (0 mg)	280 (64 mg)	280 (64 mg)
32 mg	32 mg	0	84 (32 mg)	280 (32 mg)	364 (32 mg)
64 mg	64 mg	0	84 (64 mg)	280 (64 mg)	364 (64 mg)

#### Table 3. Characteristics of the Treatment and Dosage per Fully Compliant Patient

The study drug should be administered in a single dose in the morning at approximately the same time each day, with or without food and no later than 2 PM (local time). Tablets should be swallowed whole with water and not divided, crushed, chewed, or placed in water. Patients who are fully compliant will take up to 84 tablets during the double-blind phase, and a total of up to 364 tablets for the whole study, including the 40-week extension phase. If a patient misses a dose, the dose can be taken up to 2 PM (local time) on the day of dosing. Otherwise the dose must be skipped. The next dose will be taken on the next morning. The patient must not take 2 doses in any one day.

Patients (or their designees, if appropriate) must be provided with a "study card" indicating the name of the investigational study drug, the study number, the investigator's name, a 24-hour emergency contact number, and excluded concomitant medications (e.g., QT active drugs).

# 7. TREATMENT COMPLIANCE

On Days 1 and 2, patients will receive their first dose of study drug after an overnight stay at the hospital. While out-patient, the drug will be self-administered by the patient at their residence.

The number of study drug tablets dispensed for self-administration by patients will be recorded and compared with the number returned during each scheduled visit. Patients are required to record the administration of study drug in diaries and record the time of drug intake. The diaries will be checked and verified against the pill counts and the patients will be counseled regarding compliance at every scheduled visit.

The investigator or designated study center personnel will maintain a log of all study drug dispensed and returned during the study. Patients who have < 75% compliance by Week 8 (Visit 10) may be discontinued from the study following consultation with the study medical monitor.

# 8. STUDY EVALUATIONS

## 8.1. Study Procedures

#### 8.1.1. Overview

The Time and Events Schedule that follows the Synopsis summarizes the frequency and timing of efficacy, PK, and safety measurements applicable to this study.

Additional urine pregnancy tests may be performed, as determined necessary by the investigator or required by local law or regulation, to establish the absence of pregnancy throughout the study.

During the 12-week double-blind phase, the total blood volume to be collected from each patient will be 226.5 mL: 110.5 mL for safety laboratory tests, 84 mL for PK, and 32 mL for concomitant medications.

During the 40-week open-label phase, an additional 334 mL of blood will be collected: 134 mL for safety laboratory tests, 140 mL for PK, and 60 mL for concomitant medications.

These estimates are for required blood samples and do not include additional blood samples that may be collected at the investigator's discretion for drug level monitoring or other clinical laboratory tests deemed necessary for appropriate patient care in case of occurrence of AEs (Table 4).

Phase: Type of Sample	Volume per Sample (mL)	No. of Samples per Patient	Total Volume of Blood (mL) b
12-Week Double-Blind Treatment Phase:			
Safety:			
Hematology	2	5	10
Chemistry + hormones	16	5	80
HbA1c	2	3	6
Serology c	8.5	1	8.5
Genotype	6	1	6
Concomitant Medication Evaluation	4	8	32
Pharmacokinetic	4	21	84
Subtotal		44	226.5
40-Week Open-Label Extension Phase:			
Safety (including end-of-study evaluations):			
Hematology	2	7	14
Chemistry + hormones	16	7	112
HbA1c	2	4	8
Concomitant Medication Evaluation	4	15	60
Pharmacokinetic	4	35	140
Subtotal		68	334
Total		112	560.5

#### Table 4. Estimated Blood Volume Drawna

aEstimates are based on maximum amount of blood drawn for protocol-specific procedures.

bCalculated as number of samples multiplied by amount of blood per sample.

cIncludes HBsAg, anti-HCV, and anti-HIV.

# 8.1.2. Pre-Treatment Phase

The pretreatment phase should not exceed 28 days but can be as short as 1 week.

# 8.1.2.1. Screening Period (Visit 1)

At the Screening visit, a signed informed consent form for study participation will be obtained. Informed consent must be freely given by the patient and the patient's legal representative (if applicable) and documented by signature before any procedures are performed. Screening procedures will be performed as outlined in the Time and Events Schedule that follows the Synopsis.

Screening procedures should be performed within 28 days before study drug is administered on Day 1.

Psychiatric history and diagnosis of schizophrenia will be made using the MINI and the DSM-5 Diagnostic Criteria. Patients will have a physical examination and specific laboratory tests as outlined in the Time and Events Schedules. All Screening procedures/scales should be completed and laboratory results, including genotyping, should be available prior to the Baseline visit (Visit 3).

If a patient does not meet all inclusion and exclusion criteria at initial screening visit (e.g., a screen failure), but in the future is expected to meet the eligibility criteria, the patient may be rescreened on one occasion only, as described in Section 4.

# 8.1.2.2. Hospitalization Period: Washout (Visit 2) and Baseline (Visits 3)

All inclusion and exclusion criteria will be reviewed prior to patients entering the washout phase of the study. Eligible patients will be hospitalized during the washout period and the first 2 days of treatment (washout period for 2 full days starting on Day -2; Baseline assessment on Day -1; and study Day 1 and Day 2). On Day -2 (and no earlier than Day-5), baseline safety laboratory assessments including urine drug screen and pregnancy test will be sampled. On Day -1 (Baseline or Visit 3), efficacy and the remaining safety assessments will be performed as outlined in the Time and Events Schedule. Eligibility criteria will be verified before randomization on Day 1. The results of the safety laboratory assessments including the urine drug screen as well as the analysis of the baseline ECGs by the central reader must be reviewed by the site prior to randomization. The randomization must be postponed if these results are not available for review.

# 8.1.3. Double-Blind Treatment Phase

# 8.1.3.1. Day 1/Randomization (Visit 4)

While remaining hospitalized on Day 1 (Visit 4), all patients will be randomized to 1 of 3 treatment groups: MIN-101 64 mg, MIN-101 32 mg, or placebo and will receive the first dose of study drug. Pharmacokinetic blood samples will be drawn as per the Time and Events Schedule.

# 8.1.3.2. Day 2 (Visit 5) to Week 8 (Visit 10)

Patients will be allowed to leave the hospital on Day 2, after the administration of the second dose of treatment, and after having undergone 3 ECG assessments (in triplicate) and PK evaluation performed at pre-dose and at the approximate time of  $C_{max}$  of MIN-101 and its metabolite BFB-520, and after completion of the RDQ. However, the Investigator may decide to keep the patient hospitalized as needed. RDQ will be completed prior to any authorization to leave the hospital on Day 2 or prior to any discharge authorization if later than Day 2. If discharged, patients will come back for visits at Week 1, 2, 3, 4, 8, and 12 for efficacy and safety assessments. Hospitalization on Visits 6 and 7 will be at the discretion of the investigator to ensure per-protocol ECG assessment and PK sampling are done.

# 8.1.3.3. Telephone Contacts

Participating patients or their caregivers will be contacted by phone weekly when the patients are not scheduled for site visits to inquire about the patients' well-being, compliance with treatment, and to remind them of the scheduled site visits, as appropriate. These phone calls

should occur on Weeks 5, 6, 7, 9, 10, and 11, and will utilize structured questions for that purpose.

# 8.1.3.4. Week 12 (Visit 11)

This is the last visit of the double-blind phase. Patients should be administered their last dose of the double-blind medication at this visit (i.e., study drug medication from the blister they received at Week 8). Any patient who terminates early from the study will undergo Week 12 (Visit 11) procedures. Also, patients with ongoing adverse events at the time of the EOS visit (Visit 11) will be followed until all significant changes have resolved or become medically stable.

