### • trihexyphenidyl (benzhexol)

#### Contraception

Patients who are sexually active must use, with their partner, 2 approved methods of highly effective contraception from the time of investigational medicinal product administration until 90 days after the last dose of investigational medicinal product.

The following are considered as highly effective contraception methods:

- Surgical sterilization (i.e., bilateral tubal ligation/salpingectomy, hysterectomy for female patients or partners; vasectomy for male patients or partners).
- Placement of an intrauterine device or intrauterine system.
- Hormonal contraception (implantable, patch, oral, injectable).
- Barrier methods.
  - for male patients, this must be a condom or their partner's use of an occlusive cap [diaphragm or cervical/vault caps]
  - for female patients, either their partner's use of a condom or the patient's use of an occlusive cap [diaphragm or cervical/vault caps]

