# 8.1.4.2. 40-Week Open-Label Treatment Phase

Patients who received MIN-101 during the double-blind treatment phase will continue to receive the same treatment and dose. Patients who previously received placebo will receive 1 of the 2 MIN-101 doses in 1:1 ratio per the randomization at Visit 4 (at the start of the double-blind phase). As such, the descriptor "open-label" is being used loosely to inform that all patients are receiving MIN-101 without knowledge of the dose given or the treatment received during the double-blind phase.

Hospitalization on Visits 14 and 15 will be at the discretion of the investigator to ensure per-protocol ECG assessment and PK sampling are done.

Participating patients and/or their caregivers will be contacted by phone weekly when the patients are not scheduled for site visits to inquire about the patients' well-being, compliance with treatment, and to remind them of the scheduled site visits, as appropriate. These phone calls should occur on Weeks 18, 22, 26, 30, 34, 38, 42, 46, and 50, and will utilize structured questions for that purpose.

Any patient who terminates early from this phase, and therefore from the study, will undergo the End of Treatment visit (Week 52/ Visit 26) as soon as possible. It will be followed  $\pm 2$  weeks later by the EOS visit (Week 54/Visit 27). If any of the laboratory results indicate an abnormality that warrants repeating the test, the patient should be fasting for the repeat

assessment. Patients with ongoing adverse events at the time of the EOS visit will be followed until all significant changes have resolved or become medically stable.

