# 8.4. Safety Evaluations

The collection of adverse events and concomitant medications will start after the informed consent has been signed and will continue until the follow-up visit. All safety assessments listed below will be performed as specified in the Time and Events Schedule.

Any clinically relevant changes occurring during the study must be recorded on the AE section of the eCRF.

Any clinically significant abnormalities persisting at the end of the study/early withdrawal will be followed by the investigator until resolution or until a clinically stable endpoint is reached.

The study will include the following evaluations of safety and tolerability according to the time points provided in the Time and Events Schedule:

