## 10.1. Sample Size Determination

The sample size for this study is based on the assumption of a treatment difference of 3 points in the mean change from Baseline to Week 12 in PANSS negative subscale score based on the Marder negative factor score between any MIN-101 dose group and placebo. A standard

deviation of 6.5 in the change in PANSS negative subscale score from Baseline is used. Assuming an equal allocation to placebo and each of the 2 MIN-101 doses, 100 patients in each treatment arm are required to detect the treatment difference of 3 points with a power of 90% at an overall 2-sided significance level of 0.05. When adjusted for a rate of about 40% of patients who will not have either Baseline or at least 1 on-treatment efficacy assessments, the required number of patients becomes 167 in each treatment arm. Therefore, the total number of patients enrolled across the 3 treatment arms will be 501.

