## 11.3. Procedures

## 11.3.1. All Adverse Events

All AEs, whether serious or non-serious, will be reported from the time a signed and dated informed consent form is obtained until completion of the last study-related procedure (may include contact for follow-up of safety). SAEs, including those spontaneously reported to the investigator within 30 days after the last dose of study drug, must be reported using the SAE Form. The sponsor will evaluate any safety information that is spontaneously reported by an investigator beyond the time frame specified in the protocol.

All events that meet the definition of a SAE will be reported as SAEs, regardless of whether they are protocol-specific assessments.

All AEs, regardless of seriousness, severity, or presumed relationship to study therapy, must be recorded using medical terminology in the source document and the eCRF. Whenever possible, diagnoses should be given when signs and symptoms are due to a common etiology (e.g., cough, runny nose, sneezing, sore throat, and head congestion should be reported as "upper respiratory infection"). Investigators must record in the eCRF their opinion concerning the relationship of the AE to study therapy. All measures required for adverse event management must be recorded in the source document and reported according to sponsor instructions.

The sponsor assumes responsibility for appropriate reporting of AEs to the regulatory authorities. The sponsor will also report to the investigator all SAEs that are unlisted (unexpected) and associated with the use of the drug. The investigator (or sponsor where required) must report these events to the appropriate Independent Ethics Committee/Institutional Review Board (IEC/IRB) that approved the protocol unless otherwise required and documented by the IEC/IRB.

Patients (or their designees, if appropriate) must be provided with a "study card" indicating the name of the investigational study drug, the study number, the investigator's name, a 24-hour emergency contact number, and, if applicable, excluded concomitant medications.

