## Treatment-emergent Adverse Event

Any recorded adverse event that occurs on or after the initiation of study treatment and less than or equal to 14 days after the last dose of treatment is considered treatment-emergent. Additionally, it is assumed that an adverse event which was reported to have started on Day 1 without an associated onset time may have occurred after the initiation study treatment. Hence, adverse events occurring on Day 1 without an onset time are assumed to be treatment emergent.

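### Patients who stop in the double-blind phase have no scheduled contact after Visit 11, although adverse events count as treatment-emergent up to 14 days after the last dose

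*Protocol*

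**What the plan says.** For early stopping in the double-blind phase, protocol 8.1.3.4 states: "Any patient who terminates early from the study will undergo Week 12 (Visit 11) procedures". The synopsis, protocol 3.1 and 9.2, footnote m of the double-blind schedule and SAP 1.1 ask for the same single visit, and nothing is scheduled after it. Protocol 8.1.3.4 also labels Visit 11 the EOS visit when it describes follow-up of ongoing events.

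The extension is handled differently. Protocol 8.1.4.2 states: "Any patient who terminates early from this phase, and therefore from the study, will undergo the End of Treatment visit". The same paragraph adds the EOS visit (Visit 27) about two weeks later, and footnote m of the open-label schedule asks for both visits.

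Two rules bear on how long events should be collected. Protocol 8.4 says that collection of adverse events and concomitant medications "will continue until the follow-up visit". SAP 3.3.8 defines the analysis window: an event starting on or after first treatment and "less than or equal to 14 days after the last dose of treatment is considered treatment-emergent". Protocol 10.8.1 sets the same limit from the other side, by excluding events more than 14 days after the last dose from the summary tables.

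**The concern.** The analysis window can stay open after scheduled collection has closed. For a double-blind stopper, the last study procedure is Visit 11, to be done promptly after stopping. If it falls within a few days of the last dose, nobody is scheduled to ask about new events for the rest of the 14 days. Patients who stop in the extension are seen again at about the time the window ends.

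This touches the randomised safety comparison. Protocol 9.3 withdraws patients for QTcF prolongation, suicidality and psychotic worsening. Protocol 1.5 names worsening after antipsychotic discontinuation as the main risk, and relies on frequent visits and calls to mitigate it. Scheduled contact ends at withdrawal. The clinician page of the Sheehan-STS (Attachment 11), which records a completed or attempted suicide, is used when a patient misses a scheduled follow-up visit. After Visit 11 these patients have no scheduled visit to miss. The double-blind and extension tables would share one definition of treatment-emergent but rest on different ascertainment.

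**Working it through.** **Step 1: what is scheduled after stopping.**
- Double-blind stopper: Visit 11 procedures, then nothing.
- Open-label stopper: Visit 26, then Visit 27 about two weeks later.
- The follow-up visit in protocol 8.4 does not appear in the double-blind schedule.
- Protocol 11.3.1 ends reporting at the last study-related procedure and makes a later safety contact optional.

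**Step 2: length of the gap.** Let d be the days from last dose to Visit 11. The documents set no limit on d beyond promptness. The unscheduled part of the window is max(0, 14 − d):
- d = 0: 14 days
- d = 7: 7 days
- d = 14 or more: none

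**Step 3: the plan's own total.** Inputs from protocol 10.1: difference 3, SD 6.5, two-sided alpha 0.05, power 90%, inflation 40%.
- n per arm = 2 × (1.960 + 1.282)² × 6.5² / 3² = 98.7, so 99. The plan states 100, at which power is 90.4%.
- 100 / (1 − 0.40) = 166.7, so 167 per arm.
- 3 × 167 = 501, which agrees with "Therefore, the total number of patients enrolled across the 3 treatment arms will be 501".

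**Step 4: patients affected.** The protocol gives no double-blind discontinuation rate for this trial. The nearest figure is the Phase 2b study in Table 2 (protocol 1.4.2): 244 randomised, 165 completed the double-blind phase.
- Non-completion: (244 − 165) / 244 = 79 / 244 = 32.4%.
- Wilson 95% interval: centre (p + z²/2n) / (1 + z²/n) = 0.3265; half-width z√(p(1 − p)/n + z²/4n²) / (1 + z²/n) = 0.0583. This gives 26.8% to 38.5%.
- Applied to 501: 0.3238 × 501 = 162, with a range of 134 to 193.
- On active drug: 2 × 167 = 334, and 0.3238 × 334 = 108.

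The 40% in protocol 10.1 is not used here. It is defined as patients lacking a Baseline or any on-treatment efficacy assessment, which is not a discontinuation rate.

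**Step 5: time without scheduled ascertainment, for 162 patients.**
- d = 0 for everyone: 162 × 14 = 2,268 patient-days. This is an upper bound for 162 patients.
- d = 7: 162 × 7 = 1,134 patient-days.
- d = 14: none.

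**The case against.** The strongest reply is that follow-up does exist. Adverse events ongoing at Visit 11 are followed until resolved or stable (8.1.3.4), as are clinically significant abnormalities at early withdrawal (8.4) and unresolved SAEs (11.3.2). Protocol 11.3.1 requires an SAE Form for "SAEs, including those spontaneously reported to the investigator within 30 days after the last dose of study drug". Deaths within 30 days are SAEs (11.3.2), and known pregnancies are reported and followed to outcome (11.3.3). Patients withdrawn for safety have samples and relevant assessments taken promptly (9.3). All of this stands, so a reader who infers that these patients have no contact at all goes too far. But these provisions concern events already present, events that someone reports, or assessments made around withdrawal. None schedules a question about a new event after Visit 11.

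A second reply is that 14 days is an analysis limit and does not promise active collection. That is fair. However, the extension schedule does place a visit at about that point, and 8.4 refers to a follow-up visit. The double-blind schedule is the one without it.

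A third is that the end-of-study paragraph in SAP 1.1 speaks of early withdrawal without naming a phase. It refers only to the Week 52 and Week 54 visits, and the same section gives double-blind stoppers Visit 11 alone.

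A reader might also infer that the 30-day SAE period and the contraception requirement, which runs "until 90 days after the last dose of investigational medicinal product", are left uncovered for these patients in particular. The documents do not support that. Visit 27 reaches only about day 14, so no patient has a scheduled contact at day 30 or day 90. The 90 days is a duration of contraception and not a collection period.

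**Conclusion.** The concern holds for new-onset adverse events between Visit 11 and day 14 after the last dose, in patients who stop during the double-blind phase. That rests on the text and needs no estimate. The size does need one: about 162 of 501 patients (134 to 193) if Phase 2b non-completion carries over, each with a gap of up to 14 days. A later Visit 11 shortens or removes the gap, and some of these patients will have withdrawn consent or been lost, so a call would not reach them.

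Completers who do not enter the extension would share the gap if entry is optional. Protocol 3.2 calls it an opportunity, while 3.1 and the synopsis have all patients continuing.

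A reader might infer that the safety comparison is biased between arms. The documents do not establish this. The rule is the same in all three arms, and ascertainment becomes unequal only if stopping, or the timing of Visit 11, differs by arm. Phase 2a relapse was 25% on placebo and 13% on MIN-101 (protocol 1.4.2.2), so unequal stopping is plausible, but no double-blind dropout rate by arm is given. The change is a cheap improvement worth making. The primary efficacy analysis is not affected.

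**What to change.** In protocol 3.1, 8.1.3.4, 9.2 and the double-blind schedule, add one structured telephone contact for adverse events and SAEs at or after 14 days from the last dose. It applies to every patient who stops in the double-blind phase, and to any completer who does not enter the extension, if entry is optional. The structured calls already made at Weeks 5 to 7 and 9 to 11 (8.1.3.3) can serve as the model.

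In 8.4, replace the undefined follow-up visit for these patients with that contact, and name it in 11.3.1 as the end of their adverse event collection. Then reconcile 8.1.3.4, 8.1.4.2, 8.4, 10.8.1, 11.3.1 and SAP 3.3.8 so that collection and the treatment-emergent window end together.

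The cost is protocol wording and one call per affected patient, about 134 to 193 calls on the Phase 2b assumption, plus any for completers who do not continue. Some patients will be unreachable, and a few more events will be recorded. Sample size, alpha and power stay as they are.
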